8 SUBJECTS IDENTIFIED FOR NARRATIVES

A safety narrative will be prepared for each subject who received at least one dose of troriluzole and experienced the following events (regardless of relationship to study drug):

- All deaths on-treatment and post-treatment through the end of the study
- SAEs on-treatment, which includes up to 30 days after the last dose of study drug; SAEs that occur > 30 days (i.e., during the follow-up period) will be included per the clinical judgment of the Biohaven medical monitor
- All premature discontinuations of study drug due to AEs (either identified through "action taken" or "end of treatment status")
- The following on-treatment events of special interest:
 - \circ Neutropenia based on laboratory results and defined as minimum absolute neutrophil count < 500 per mm³
 - LFT abnormalities:
 - ALT or AST > 3x ULN
 - ALT or AST > 3x ULN, and serum total bilirubin $\ge 2x$ ULN
 - Interstitial lung disease Standardized MedDRA Query (SMQ) including eosinophilic pneumonia

These select events are described in the current version (v3) of the Biohaven Safety Narrative Scope for BHV4157 (troriluzole). Because select events may be subject to change, updates to the list of

CONFIDENTIAL

events or selection algorithms after database lock may be described in a Note to File (NTF) rather than amending the SAP.

A by-subject listing of safety narrative subject identifiers will be presented for all screened subjects with the select events as described above

9 AD HOC ANALYSES

Additional analyses of interest not specified directly in the SAP were analyzed using the FAS. These analyses were performed on the following data cuts:

• Randomization Phase: locked data through Extension Phase Week 48

Randomization Phase

DocuSign Envelope ID: BD8AB61B-7989-408F-A5B1-B84E58727CD3

Biohaven Pharmaceuticals Protocol BHV4157-201 SAP ver 04.0 Addendum 27Mar2020

Extension Phase – Week 48

CONFIDENTIAL

10 UPDATES TO ANALYSES SPECIFIED IN THE SAP

The following updates were made to the SAP (v2) specified analyses:

27Mar2020

12

11 ADVERSE EVENTS

Treatment-related AEs are defined as any AE considered unlikely related, possibly related, or related. This is an update to Section 4.8.2 of the SAP (v2.0) where AEs related to treatment were only inclusive of those considered definitely related, probably related, or possibly related. This has been updated to match the options in the Case Report Form (CRF).

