- Admission encountered for another life circumstance that carries no bearing on health and requires no medical intervention (i.e., lack of housing, care-giver respite, family circumstances).

Disability/incapacitating: An AE is incapacitating or disabling if the experience results in a substantial and/or permanent disruption of the subject's ability to carry out normal life functions.

Classification of Adverse Events

The severity of all AEs must be recorded in the eCRF and on the SAE Form, if applicable. The severity or intensity of an AE refers to the extent to which it affects the subject's daily activities. The severity of events should be graded as mild, moderate or severe. Refer to the BHV4157-201 SAE Reporting and Management Plan for definitions of each grading criteria.

The Investigator's assessment of an AEs relationship to study drug is part of the documentation process but is not a factor in determining what is or is not reported in the study. If there is any doubt as to whether a clinical observation is an AE, the event should be reported. The relationship or association of the study drug in causing or contributing to the AE will be characterized as either not related, unlikely related, possibly related, or related. Refer to the BHV4157-201 SAE Reporting and Management Plan for definitions of each criteria.

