2.4. Efficacy, Safety, and Other Variables

2.4.1. Efficacy Variables

Primary Endpoint

• Change from baseline to Week 8 in SARA total score

Secondary Endpoints

- Frequency and severity of adverse events (AEs) and discontinuation due to AEs
- Patient impression of benefit via use of PGI-C at Week 8

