4.8.2. Adverse Events

Adverse eventss will be coded using MedDRA and displayed in tables and listings by system organ class (SOC) and preferred term (PT).

Analyses of AEs will be performed for those events that are considered treatment-emergent, where treatment-emergent is defined as any AE that developed, worsened, or became serious after first dose of test treatment.

Adverse events are summarized by subject incidence rates; therefore, in any tabulation, a subject contributes only once to the count for a given AE (SOC or PT).

The number and percentage of subjects with the following on-treatment AEs will be summarized by treatment group and overall for the Randomization and Extension Phases, separately.

- Treatment-emergent AEs,
- AEs related to treatment (definitely, probably, or possibly),
- SAEs,
- AEs with Grade 2 or greater severity,
- AEs leading to discontinuation, and
- Standardized MedDRA query (SMQ) of interstitial lung disease, including eosinophilic pneumonia

On-treatment AEs are AEs with a start date prior to 30 days after the last dose of study drug. For the Randomization Phase, treatment-emergent AEs will be assessed from the date of randomization until: 1) the first day of the Extension Phase or 2) if the subject did not continue into the Extension Phase, 30 days after the last dose of study drug. For the Extension Phase, treatment-emergent AEs will be assessed from the first day of the Extension Phase until 30 days after the last dose of study drug.

In the above tabulations, each subject will contribute only once (i.e., the most related occurrence or the most severe occurrence) to each of the incidence rates in the descriptive analysis, regardless of the number of episodes. No formal hypothesis-testing analysis of AEs incidence rates will be performed.

All AEs occurring pre-treatment, during the Randomization phase, during the Extension phase, and throughout the entire study will be listed. Additional listings will be provided for the Randomization and Extension Phases, including deaths, SAEs, and AEs leading to withdrawal of study drug.

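### The SAP addendum counts adverse events rated unlikely related as treatment-related, and its stated reason, matching the CRF, does not require that

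*SAP*

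**What the plan says.** Protocol section 8.1.2, under the classification of adverse events, has the investigator rate causality on four levels. The relationship is "characterized as either not related, unlikely related, possibly related, or related". The definitions of those levels are left to a separate SAE reporting and management plan.

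SAP v2.0, section 4.8.2, plans a by-arm table for each phase of "AEs related to treatment (definitely, probably, or possibly"). In these tables "each subject will contribute only once (i.e., the most related occurrence or the most severe occurrence").

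Section 11 of the addendum, dated 27 March 2020, replaces the v2.0 rule: "Treatment-related AEs are defined as any AE considered unlikely related, possibly related, or related". The reason given is: "This has been updated to match the options in the Case Report Form (CRF").

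**The concern.** Two of the three v2.0 terms, definitely and probably, are not on the protocol's scale, so some relabelling was needed. The addendum goes further and reclassifies events that the investigator judged unlikely to be due to the drug. That a category exists on a form does not settle which side of the related/unrelated line it belongs on: *not related* is on the protocol's scale too, and it stays outside.

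Safety and tolerability is a stated secondary objective, and related AEs are one of its planned summaries. Under the addendum the table reports everything except *not related*, but under the title of treatment-related. A reader would not expect that. The risk of misreading is greatest in the open-label Extension Phase, where no concurrent placebo arm puts a raised rate in context.

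The addendum also refers to Randomization Phase data as already locked. The documents do not show who was unblinded at that point, and nothing improper is implied. A late change to a safety definition should still carry a reason that accounts for it.

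**Working it through.** **Inputs.** The causality scale is from protocol 8.1.2, the v2.0 rule and the counting rule from SAP 4.8.2, and the current rule from addendum section 11. About 120 subjects randomized 1:1 (protocol 5.1 and 7.2.1) gives about 60 per arm. The plan states no AE rate, so there is no figure of its own to reproduce.

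**Step 1: the rules side by side.**

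| Protocol level | v2.0, with definitely and probably mapped to *related* | Addendum |
|---|---|---|
| not related | no | no |
| unlikely related | no | **yes** |
| possibly related | yes | yes |
| related | yes | yes |

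The middle column uses only levels on the protocol scale, so it already fits that scale. The two rules differ in the second row alone.

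**Step 2: direction.** A subject's events can cover any subset of the four levels, which gives 2^4 = 16 profiles. Counting a subject who has at least one qualifying event:

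- Against the mapped v2.0 rule, the addendum never counts fewer. It counts more in 2 profiles: unlikely only, and not plus unlikely.
- Against v2.0 read literally on the four-level scale, where only *possibly* survives, it again never counts fewer, and it counts more in 6 profiles.

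Let u be the share of subjects in an arm whose most related event is *unlikely related*. Then, against the mapped rule:

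addendum rate = v2.0 rate + u, with u ≥ 0.

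The two rates are equal only if u = 0.

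**Step 3: size, under assumed rates.** Let a and b be the shares with a possibly related or related event on drug and placebo, and u_d and u_p the additions. The addendum rates are a + u_d and b + u_p. Take a = 30% (18 of 60) and b = 15% (9 of 60).

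| u_d, u_p | Drug vs placebo | Subjects (of 60 each) | Difference (points) | Ratio |
|---|---|---|---|---|
| 0, 0 | 30% vs 15% | 18 vs 9 | 15 | 2.00 |
| 10%, 10% | 40% vs 25% | 24 vs 15 | 15 | 1.60 |
| 20%, 20% | 50% vs 35% | 30 vs 21 | 15 | 1.43 |
| 30%, 30% | 60% vs 45% | 36 vs 27 | 15 | 1.33 |
| 20%, 10% | 50% vs 25% | 30 vs 15 | 25 | 2.00 |
| 30%, 10% | 60% vs 25% | 36 vs 15 | 35 | 2.40 |
| 10%, 20% | 40% vs 35% | 24 vs 21 | 5 | 1.14 |

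The difference is unchanged only if u_d = u_p. The ratio falls only if u_d/u_p < a/b, which here is 2.0. Both arms' rates rise in every row after the first, but the contrast between them has no fixed direction.

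**The case against.** The best defence is that this is an open choice. The addendum states the old rule, the new rule and the section it replaces. Counting everything except *not related* is a recognisable inclusive convention in safety reporting, because an unlikely rating does not exclude a drug contribution. The CRF and the plan that defines the causality levels are not among the documents, and the mapping of definitely and probably to *related* is natural but written down nowhere. The v2.0 rate is also a counterfactual, since its terms could not be applied literally to ratings on the protocol's scale.

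The consequence is narrow as well. The secondary safety endpoint is "Frequency and severity of adverse events (AEs) and discontinuation due to AEs", which does not use relatedness. The SAP adds: "No formal hypothesis-testing analysis of AEs incidence rates will be performed". Narratives are selected "regardless of relationship to study drug". The all-causality, SAE and discontinuation tables do not depend on the definition, and neither does any efficacy result.

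Most of this stands as a limit on the consequence. It does not supply the missing reason. The addendum neither claims to be taking a conservative view nor cites the definitions plan; it cites only the form. The direction of the change is the same under either reading of v2.0. The lack of comparability is conditional: if no subject has *unlikely related* as the most related rating, the two rules give the same rates.

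**Conclusion.** The concern holds. As written, the addendum produces an all-except-not-related rate under a treatment-related label, and the stated justification does not support that step. That the rates will be equal to or higher than under v2.0 follows from set inclusion. The increase is u in each arm, which the documents do not give. In the assumed cases above, with u from 10% to 30%, it is 6 to 18 extra subjects per arm of 60. The drug-placebo contrast could shrink, hold or grow.

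This rests on inferring the CRF options from protocol 8.1.2 and the addendum's own wording. The problem is limited to descriptive related-AE summaries, but it should be corrected before those tables are relied on.

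**What to change.** In section 11 of the addendum, define treatment-related AEs as those recorded as *possibly related* or *related*. Keep the inclusive view as a separately labelled supplementary table, either as all events except *not related* or, better, as all four causality levels by arm and phase. Footnote the definition on each related-AE table.

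Adding only a rationale and a footnote to the present rule would not be enough, because the main table would still carry a label that does not match its content.

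The cost is one sentence in the addendum and a re-run of the related-AE tables, with no new data.

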12 LABORATORY DATA

In addition to AEs of special interest (i.e., interstitial lung disease), specified in Section 4.8.2 of the SAP (v2.0), the following on-treatment events are of special interest:

- Neutropenia based on laboratory results and defined as the minimum absolute neutrophil count $<0.5\times10^9/L$
- Liver function test abnormalities:
 - \circ ALT or AST > 3x ULN
 - ALT or AST > 3x ULN and serum total bilirubin \ge 2x ULN

CONFIDENTIAL

1. INTRODUCTION AND OBJECTIVES OF ANALYSIS

1.1. Introduction

This document presents the statistical analysis plan (SAP) for Biohaven Pharmaceuticals, Protocol BHV4157-201: A Phase IIb/III, Randomized, Double-blind, Placebo-controlled Trial of BHV-4157 in Adult Subjects with Spinocerebellar Ataxia.

This SAP is based on Amendment 4 to the final protocol dated July 27, 2017. It contains the analysis details and methodology to answer the study objectives, including planned summary tables, by-subject listings, and figures, which will provide the basis for the results section of the clinical study report (CSR). Operational aspects related to collection and timing of planned clinical assessments are not repeated in this SAP unless relevant to the planned analyses.

1.2. Objectives of Statistical Analysis

Primary Objective

• To compare the efficacy of BHV-4157 (140 mg once daily) versus placebo on ataxia symptoms in subjects with spinocerebellar ataxia (SCA) after 8 weeks of treatment as measured by the total score on the Scale for the Assessment and Rating of Ataxia (SARA)

Secondary Objectives

- To assess of the safety and tolerability of BHV-4157 in subjects with SCA
- To compare efficacy of BHV-4157 with placebo on patient impression of benefit via use of the Patient Global Impression of Change (PGI-C)

2. STUDY DESIGN

2.1. Synopsis of Study Design

BHV4157-201 is a Phase IIb/III, multicenter, randomized, double-blind, 2-arm placebocontrolled parallel-group study designed to assess safety, tolerability, and efficacy signals in a population of subjects with SCA.

Subjects who are determined to be eligible for the study will enter the Randomization Phase. Dosing will continue for 8 weeks. Subjects will return to the clinic 2 weeks after discontinuing study medication for a follow-up safety visit (see Figure 1). In addition, subjects completing the Randomization Phase will be offered 48 weeks of open-label treatment given the principle investigator believes open-label treatment offers an acceptable risk-benefit profile. Subjects who agree to enter the Extension Phase will not be required to wash-out of drug or complete the follow-up safety visit, but instead should continue dosing as specified in the Extension Phase.

Subjects entering the Extension Phase will have their first Extension visit 4 weeks after the Week 8 Randomization Phase visit. If there is a delay of two weeks or more in dosing between the Randomization Phase and the Extension Phase, then subjects will be required to complete an Extension baseline visit. Thereafter, subjects will undergo visits every fourth week through Week 12 of this phase. Then subjects will undergo visits every 12 weeks up to Week 48 of this phase. All subjects will undergo a post study drug termination visit two weeks after the last dose of study drug in the Extension Phase.

2.2. Randomization Methodology

Subjects will be randomized to receive placebo once daily (QD) or BHV-4157 (140 mg QD),

2.3. Unblinding

Blinding is critical to the integrity of this clinical study. However, in the event of a medical emergency or pregnancy, in which knowledge of the investigational product is critical to the subject's management, the blind for that subject may be broken by the treating physician. The unblinded biostatistician, or designee, will be unblinded to the randomized treatment assignments. A PK and interactive web response system (IWRS) randomization manager may also be unblinded. Except as noted above, members of the Biohaven research team will remain blinded.

Figure 1: Study Schematic

R=Randomization

2.4. Efficacy, Safety, and Other Variables

2.4.1. Efficacy Variables

Primary Endpoint

• Change from baseline to Week 8 in SARA total score

Secondary Endpoints

- Frequency and severity of adverse events (AEs) and discontinuation due to AEs
- Patient impression of benefit via use of PGI-C at Week 8

2.4.4. Safety and Other Variables

Safety assessments performed during the study include AEs, laboratory evaluations, physical examinations, vital signs and physical measurements, 12-lead electrocardiograms (ECGs), concomitant medications, and the Sheehan-Suicidality Tracking Scale (S-STS).

3. SUBJECT POPULATIONS

3.1. Population Definitions

The following subject populations will be evaluated and used for presentation and analysis of the data:

Full Analysis Set (FAS): All randomized subjects with at least 1 dose of study treatment and a baseline and post-baseline total SARA score during the Randomization Phase.

Per Protocol (PP) Set: All FAS subjects without any major protocol deviations.

Safety Analysis Set: All subjects who received at least 1 dose of study treatment.

3.2. Protocol Deviations

Any significant event that does not comply with the inclusion/exclusion criteria, study conduct (e.g., inadequate informed consent, unreported SAEs), or study procedures (e.g., use of prohibited medications as defined by the protocol; improper breaking of the blind; overall non-compliance with study medication <80% for either the Randomization Phase or both phases, calculated prior to database lock) will be documented as a major deviation.

All protocol deviations will be presented in the data listings.

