7.4 Treatment Compliance

Responsible study personnel will dispense the study drug. Accountability and compliance verification should be documented in the patient's study records.

Patients have to be counseled on the importance of taking the study drug as directed at all study visits. If poor compliance continues, (i.e., multiple missed doses resulting in less than 80% overall compliance during the Randomization Phase), discontinuation of the patient from the trial should be considered.

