4.6. Efficacy Evaluation

Unless otherwise noted, all efficacy analyses will be conducted using the FAS and PP populations as outlined below. All efficacy data will be included in listings by subject, study medication, and visit (as applicable) for the Randomization and Extension phase, separately.

For the Randomization Phase, baseline is considered as the last visit prior to dosing (Visit 2 assessment); and for the Extension Phase, baseline is considered as the visit prior to Extension Visit 1:

- If less than 14 days elapsed between the Randomization and Extension Phases, then use the Visit 4 (Week 8) assessment during the Randomization Phase, or
- If 14 or more days elapsed between the Randomization and Extension Phases, then use the Repeat Baseline assessment at the beginning of the Extension Phase.

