4.8.1. Extent of Exposure and Compliance to Study Treatment

Subjects will receive placebo (QD) or BHV-4157 (140 mg QD) during the Randomization phase. Subjects who complete 8 weeks of treatment in the Randomization phase may be eligible for an open-label Extension phase of the study.

For the Randomization phase, the extent of subject exposure to study treatment will be quantified as the number of days on study drug (placebo or BHV-4157) and measured from the time the subject received the first dose until the time the subject received the last dose, either at the end of 8 weeks of treatment or withdrawal from the Randomization phase.

For the Extension phase, the extent of subject exposure to study treatment will be quantified as the number of days on study drug (BHV-4157) and measured from the time the subject received the first dose of BHV-4157 until the time the subject received the last dose, either at the end of the study or withdrawal from the Extension phase.

The number of tablets taken will be summarized for both the Randomization and Extension phases, separately. Additionally, percent (%) compliance will be calculated and summarized as follows:

Randomization phase % compliance = number of tablets taken during the Randomization phase / (last dose date – first dose date + 1) \times 100.

Extension phase % compliance = number of tablets taken during the Extension phase / (last dose date – first dose date + 1) \times 100.

Overall % compliance = number of tablets taken during the study / [(last dose date – first dose date + 1) – (number of days with a dosing break in dosing between the Randomization and Extension phases)].

Study drug administration and compliance will be listed in subject data listings for the Randomization and Extension Phases, separately.

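### Open-label doses missed after Week 8 can remove a subject from the per-protocol sensitivity analysis of Week 8 SARA

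*SAP*

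**What the plan says.** SAP 3.2 gives examples of events to be recorded as major deviations. One is "overall non-compliance with study medication <80% for either the Randomization Phase or both phases, calculated prior to database lock".

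SAP 3.1 then defines the "Per Protocol (PP) Set: All FAS subjects without any major protocol deviations". There is one such set, with no phase or time limit. The FAS definition in the same section does carry a limit: "All randomized subjects with at least 1 dose of study treatment and a baseline and post-baseline total SARA score during the Randomization Phase".

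SAP 4.6 states: "Unless otherwise noted, all efficacy analyses will be conducted using the FAS and PP populations as outlined below". The primary endpoint, change from baseline to Week 8 in SARA total score, is therefore analysed on PP as well as FAS. SAP 4.2.5 classes the PP results as sensitivity analyses outside the multiplicity control.

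SAP 4.8.1 gives a compliance formula for each phase, including "Randomization phase % compliance = number of tablets taken during the Randomization phase" over the days from first to last dose, and a combined one: "Overall % compliance = number of tablets taken during the study / [(last dose date – first dose date + 1", less any dosing break between the phases. The combined formula counts extension tablets.

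Protocol 7.4 applies its 80% figure to the blinded phase alone: "multiple missed doses resulting in less than 80% overall compliance during the Randomization Phase".

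**The concern.** A PP analysis is meant to show the effect in subjects who followed the protocol over the period being measured. For Week 8 SARA that period ends at Week 8. A dose missed afterwards cannot change a score already recorded, so excluding subjects for it does not make the set more adherent over those 8 weeks. It makes membership depend on events after the outcome, in an open-label phase where former placebo subjects first receive active drug. Exclusions could therefore differ by randomized arm, although nothing in the documents gives a direction or size.

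The lock is also unnamed. SAP 4.3 has the double-blind data unblinded and analysed after the last subject completes or leaves the 8 weeks, and the extension summarised later. The natural reading of SAP 3.2 is the lock for the Week 8 analysis. On that reading, early enrollees bring more extension time into the calculation than late ones, so two subjects with the same dosing behaviour can be classified differently because of enrolment date. Under a later lock, up to the full extension could count.

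At stake is whether the PP result can serve as a check on the primary result, and whether two programmers would build the same PP set.

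**Working it through.** **The plan's own figure.** SAP 4.1 states about 90% power for 56 per group, difference 1.24, SD 2.01, two-sided alpha 0.05. An exact two-sample t-test calculation gives 89.9%, so the figure reproduces. It does not involve the PP set, so this point leaves it unchanged.

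**Meaning of the both-phases limb.** If it meant below 80% in each phase separately, the Randomization Phase limb would already exclude the subject and the second limb would add nothing. The combined reading gives it content and matches the overall formula in SAP 4.8.1.

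**Inputs.** The blinded phase is 56 days (8 weeks, SAP 2.1). For the extension, SAP 2.1 says "subjects completing the Randomization Phase will be offered 48 weeks of open-label treatment", which is 48 × 7 = 336 days. Dosing is once daily and the cut-off is 80% (SAP 3.2). Assumptions: no dosing break, and all 56 blinded doses taken.

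**Formula.** Let D be the extension days from first to last extension dose, and c the proportion of those doses taken. Overall compliance is (56 + D·c)/(56 + D). It falls below 0.80 when

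c < [0.8 × (56 + D) − 56]/D,

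or equivalently when the missed extension doses exceed 0.2 × (56 + D).

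| D (days) | Threshold c | Fewest missed doses for exclusion | Overall compliance at that point |
|---|---|---|---|
| 14 | 0.000 | impossible (missing all 14 gives exactly 80%) | – |
| 28 | 0.400 | 17 | 67/84 = 79.8% |
| 84 | 0.667 | 29 | 111/140 = 79.3% |
| 168 | 0.733 | 45 | 179/224 = 79.9% |
| 336 | 0.767 | 79 | 313/392 = 79.8% |

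**Dependence on accrued time.** Take the same subject at a constant 75% in the extension. The 80% line is reached at D = 56 × 0.2/(0.80 − 0.75) = 224 days.

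- D = 168: (56 + 126)/224 = 182/224 = 81.3%, kept.
- D = 224: (56 + 168)/280 = 224/280 = 80.0%, on the line and kept.
- D = 252: (56 + 189)/308 = 245/308 = 79.5%, excluded.
- D = 336: (56 + 252)/392 = 308/392 = 78.6%, excluded.

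**Early stopping.** The denominator ends at the last dose, so leaving the extension early does not in itself lower compliance. A subject who takes 63 of 84 extension doses and then stops has (56 + 63)/(56 + 84) = 119/140 = 85.0% and is kept.

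**Under a Randomization Phase rule.** With 56 days of dosing, 45/56 = 80.4% passes and 44/56 = 78.6% fails. A subject at 56/56 stays in the Week 8 PP set whatever happens later.

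**The case against.** The strongest answer is that a phase-matched rule was intended: blinded-phase compliance for Week 8 analyses, overall compliance for extension analyses. The SAP reports disposition, safety and compliance by phase, sets separate baselines for each, and the Protocol ties its 80% figure to the Randomization Phase. This is plausible. It is written nowhere visible, however, and the rule as it stands joins the two limbs with an either/or and feeds one PP set.

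Second, the public copy has gaps where a limit could sit: SAP 4.2.4 and 4.2.6, the end of 4.6.1, and addendum sections 4 (analysis sets, only partly visible) and 10 (updates to SAP analyses). SAP 4.6 also allows exceptions. This stands as a limit on confidence: the conclusion concerns the visible text.

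Third, at a Week 8 lock few subjects could have 336 extension days, so the 308/392 example is an upper case. That is fair. At 28 days a fully compliant subject must miss 17 doses to be excluded, and at 14 days or fewer exclusion cannot happen. The documents give no accrual period with which to say how many subjects would have long extension exposure at that lock. Addendum section 9 names data locked through Extension Week 48, but for ad hoc FAS analyses.

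Fourth, compliance is one item in a list of examples of significant events, which may leave room for judgement, and calculating it before lock already fixes it in time on the Week 8 reading. But the item states a numerical cut-off, and fixing it before lock does not remove the extension doses from it.

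**Conclusion.** The point holds as a minor one. On the visible text, SAP 3.1, 3.2 and 4.6 together let doses missed after the Week 8 assessment exclude a subject from the PP analysis of that assessment, and the amount of extension time counted depends on a lock that is not named.

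The effect is confined to a sensitivity analysis. The primary MMRM on the FAS, its alpha and the stated power are untouched. For a subject with full blinded-phase compliance, exclusion needs substantial extension non-adherence: at least 17 of 28, 29 of 84 or 79 of 336 doses missed before the last dose. No number of excluded subjects, and no direction or size of bias, can be given from the documents.

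This rests on the combined reading of the both-phases limb, once-daily dosing with no break between phases, and no contrary text in the blank sections. Confidence is medium because of those blanks.

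**What to change.** For all Week 8 analyses, define PP in SAP 3.1 as FAS subjects with no major deviation through the Week 8 visit and Randomization Phase compliance of at least 80% (at least 45 of 56 doses for a subject dosed for the full 8 weeks). Freeze membership before the double-blind data are unblinded. Keep the both-phases criterion only for a separately defined PP set for extension analyses, if one is wanted. State in SAP 3.2 which database lock is meant.

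If the data are already unblinded, report which rule and which lock were used, and rerun the PP analysis on Randomization Phase compliance. If a phase-matched rule was always applied, one sentence saying so settles the matter.

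The cost is two or three lines of SAP text and a phase-specific deviation flag. SAP 4.8.1 already calculates Randomization Phase compliance separately, so no new data are needed.
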